7.0 RISKS

Patients undergoing AF ablation are at risk for complications by nature of the procedure. These risks are inherent to the patient population studied here. The risks of obtaining blood samples from phlebotomy of peripheral veins and existing venous lines are minimal.

One risk of donating samples for genetic research may be the release of information that could link the patient to the stored samples and/or the results of the tests run on those samples. The release of this information could cause problems with insurance or future employment. We have mechanisms in place to protect against such risks.

8.0 REPORTING OF ADVERSE EVENTS OR UNANTICIPATED PROBLEMS INVOLVING RISK TO PARTICIPANTS OR OTHERSData and Safety Monitoring Plan

Oversight of the data and safety monitoring plan will be provided by a Data and Safety Monitoring Board (DSMB). The DSMB will meet at least twice a year and review data on adverse events, adverse drug reactions, data quality, and study recruitment. DSMB reports will be sent to the IRB at least yearly.

Data Safety Monitoring Board (DSMB) will be formed to review safety data, study progress, and data quality every 6 months or after enrollment of every 30 subjects, whichever occurs earlier. The DSMB will be chaired by [name], MD, MPH Associate Professor of Medicine, Director, Nonalcoholic Fatty Liver Disease Program, Columbia University – NY Presbyterian Hospital; an external member will be [name], MD, MPH, Professor of Medicine, Brigham and Women's Hospital, Director of the Center for Arrhythmia Prevention, who has expertise in clinical trials of AF; and a biostatistical member, [name], who has expertise in biostatistical review for DSMBs. The DSMB will review all serious adverse events (AEs). Any serious AE will be reported to the DSMB, IRB, and FDA as soon as possible, but not more than three days from the investigators' awareness of the event. Any untoward medical event will be classified as an AE, regardless of its causal relationship with the study.

Reporting of Adverse Events or Unanticipated Problems involving Risk to Participants or Others:

Definitions of adverse events: an adverse event (AE) is "any untoward medical occurrence in a patient or clinical investigation subject administered a pharmaceutical product and which does not necessarily have a causal relationship with this treatment".

Adverse events include:

- Worsening (change in nature, severity or frequency) of conditions present at the onset of the trial
- Patient / subject deterioration due to the primary illness
- Intercurrent illnesses
- Drug interactions
- Events related or possibly related to concomitant medications
- Abnormal laboratory values or changes of vital signs, as well as significant shifts from baseline within the range of normal, which the Investigator considers clinically significant.

Unexpected Adverse Drug Reaction: an unexpected Adverse Drug Reaction is “an adverse reaction, the nature or severity of which is not consistent with the applicable product information (e.g., Investigator’s Brochure for an unapproved investigational medicinal product)”. Definitions of serious adverse events or serious adverse drug reaction: during clinical investigations, adverse events may occur which, if suspected to be drug-related (adverse drug reactions), must be significant enough to lead to important changes in the way the medicinal product is developed (e.g., change in dose, population, needed monitoring, consent forms). This is particularly true for reactions, which, in their most severe forms, threaten life or function.

A serious adverse event/experience (SAE) or reaction is any untoward medical occurrence that at any dose:

1. results in death
2. is life-threatening
3. requires inpatient hospitalization or prolongation of existing hospitalization
4. results in persistent or significant disability/ incapacity (as per reporter’s opinion)
5. is a congenital anomaly/birth defect
6. is another medically important condition
7. The term "life-threatening" in the definition of "serious" refers to an event in which the patient is at risk of death at the time of the event; it does not refer to an event which hypothetically might have caused death if it were more severe.

Important medical conditions that may not result in death, be life-threatening, or require hospitalization may be considered as SAEs when, based upon appropriate medical judgment, they may jeopardize the patient or may require intervention to prevent one of the outcomes listed in the definition above. Examples of such events are intensive treatment in an emergency room or at home for allergic bronchospasm; blood dyscrasias or convulsions that do not result in hospitalization; or development of drug dependency or drug abuse.

Definition of severity of adverse events:

Mild: Causing no limitation of usual activities; the subject / patient may experience slight discomfort.

Moderate: Causing some limitation of usual activities; the subject / patient may experience annoying discomfort.

Severe: Causing inability to carry out usual activities; the subject / patient may experience intolerable comfort or pain.

Definition of adverse event causality:

The Investigator will determine causality of each adverse event by using the classification criteria: unlikely, likely, or not assessable.

Unlikely: The AE is considered by the Investigator to be due to a pre-existing condition, a known manifestation of the target disease, a recurrent condition, or is likely explained by environmental or diagnostic therapeutic factors or was pre-existing and did not deteriorate.

Likely: The AE occurred during or after administration of the study treatment or a pre-existing event worsened within an appropriate period of time, and at least one of the following criteria is applicable:

- o the event could not be explained by the clinical condition or history of the subject, environmental or toxic factors, or other diagnostic or therapeutic measure;
- o was an expected ADR associated with study treatment or a class-labeled drug effect;
- o AE subsided or disappeared after withdrawal or dose reduction of study treatment; or
- o AE recurred after re-exposure to study treatment.

Not assessable: There is insufficient or conflicting evidence for classifying the causality of the AE as likely or unlikely. Lack of information may apply for this situation.

Note: AEs with causality 'likely' or 'not assessable' are considered to be 'possibly drug-related.'

Adverse event reporting

Any adverse events (AEs) will be reported to the PI within 72 hours of notification of the event. The PI will notify the DSMB of any major adverse events. Any unanticipated problems involving risk to the participants or others will be discussed with the PI and DSMB. Non-serious AEs and incidences of noncompliance with the protocol will be reported to the IRB at the time of annual review.

Serious Adverse Events (SAEs) will be reported according to the following procedure:

The occurrence of serious adverse events will be reported to the Investigator within 24 hours after notification of their occurrence. The Investigator will report SAEs to the DSMB and the Vanderbilt University Medical Center Institutional Review Board within 7 days of the Investigator's notification of the event.

In an unanticipated event of prolonged side effect, requiring prolongation of hospital stay, patients will be retained in the hospital until side effects have resolved. For minor side effects, where inpatient care is deemed unnecessary, follow-up will be maintained via phone or as outpatient if necessary. Patient and their families will be given the PI's contact number for reporting any other effects of medication following discharge.

Any newly discovered information which may affect the subject or their caregiver's decision to continue to participate in the study will be passed on to them as soon as possible. This may also result in a change to the consent form and review by the IRB.

9.0 STUDY WITHDRAWAL/DISCONTINUATION

Participants may withdraw from the study at any time by informing the study staff verbally or in writing. If an individual withdraws their consent, we will withdraw the participant. Contact information for the PI and study staff will be made available to the participant upon enrollment in the consent document. Any remaining biological samples and data will be destroyed. Any data or biological samples that have been used for research prior to their withdrawal request will not be withdrawn and destroyed.

A participant may be withdrawn from the study by the PI if any of the following occurs:

- i. The participant, for any reason, does not undergo AF ablation.
- ii. The participant does not comply with the study protocol, such as failure to attend research encounters, or inability to wear the smartwatch.
- iii. The participant experienced an adverse event related to the study drug/protocol necessitating withdrawal.

10.1. Aim 1 (Clinical Endpoint)

The primary hypothesis will test whether 2-HOBA reduces the rate of early recurrence of AF, atrial tachycardia, or atrial flutter following AF ablation within 28 days follow-up. For simplicity we will refer to this as "AF recurrence".

Measurement of Outcome (Aim 1): Participants enrolled in the study will wear a smartwatch linked to an iPhone to continually record heart rate, variability and detection of arrhythmias. For detection of the primary endpoint, participants will record a daily ECG each morning upon waking via the watch. In addition, participants will be notified by the smartwatch of 1) detection of atrial fibrillation or atrial flutter, 2) persistent high HR (> 110 bpm) outside of exercise. Upon prompting or upon patient self-report of symptoms, participants will utilize the ECG capture function of the watch and record the ECG for study personnel. A continuous tracing of 30 seconds (the full duration of a Watch EKG tracing) will be considered as having met the primary endpoint.

Sample size and power (Aim 1): The sample size of this study is based on a logistic regression of the binary primary endpoint of early AF recurrence by the end of follow-up. A total sample size of 162 with 81 in each arm will provide 81% power to detect a reduction in the rate of early recurrence of AF if the event rate is 29% in the treatment arm. This change corresponds to an odds ratio of 0.4 (treatment vs control), which is nearly equivalent to the odds ratio observed in similar trials using colchicine (colchicine OR 0.38)²⁶ at the significance level of 0.046 using a 1-sided Farrington and Manning likelihood score test, and a 48% rate of early recurrence in the placebo (control) group. The estimate 48% rate of early recurrence was extrapolated from our pilot data, which found a 45% rate of recurrence, but did not utilize continuous monitoring as will be performed in our trial. An interim analysis will be performed for superiority after half of the patients (n=40 per group) have completed their 28-day assessment of the primary endpoint at the significance level of 0.006. The final analysis will be performed after all patients have completed their 28-day assessment of the primary point at two-sided significance level of 0.041. Efficacy will be declared early at the interim analysis if the efficacy boundary is crossed ($p < 0.007$). All on-study patients will be followed for efficacy and safety until the planned end-of-follow-up. If the interim analysis indicates that the treatment is not better than the control by 13% (non-binding futility boundary $p > 0.4$), we may close the recruitment into study with regard to any recommendations of DSMB. The O'Brien-Fleming boundaries was used for the alpha- and beta-spending functions to preserve the overall Type I and Type II error.

Primary Analysis (Aim 1): All FAS will be included in the primary analysis of AF recurrence, the primary efficacy endpoint. Binary recurrence of AF will be compared between treatment and control using a chi-square test. The primary analysis will be performed using a multivariable logistic regression model, where the dependent/outcome variable is the early AF recurrence (yes/no) by the end of the 28-day follow-up and the primary independent/predictor variable is the treatment arm (2-HOBA or placebo). Adjustment will be made for age, gender, AF type (paroxysmal versus persistent), method for pulmonary vein isolation (radiofrequency versus cryoablation), additional ablation lesions (yes/no), BMI (continuous), and hours of monitoring (0-672 hours). To avoid over-fitting our multivariable logistic regression model, a 10:1 ratio for degrees of freedom per the less frequent outcome event will be used in our modeling. Nonlinear form of the continuous predictors (age, BMI, and hours of monitoring) will be considered when building the model with restricted cubic splines. Models will be evaluated for goodness-of-fit, and internally validated for the calibration and discrimination performance using the bootstrap method.

Secondary Analysis (Aim 1): A secondary analysis will analyze a surrogate of AF burden as the endpoint and designed to account for the impact of cardioversion on AF burden assessment. AF burden is the percentage of time in AF, atrial tachycardia, or atrial flutter over total time monitored. The secondary analysis will use the data

provided by the continuous HR monitor provided by the smartwatch. The analysis will be performed using a linear mixed models (LMM) in which the AF burden is assessed weekly during the 4-week (28-day) follow-up period. Same covariates mentioned in the primary analysis will be considered. Additionally, AF burden will also be analyzed in ordinal scale using generalized estimating equation (GEE), ranked based on severity according to increasing AF burden and whether or not a cardioversion was performed. For any missing data in the covariates, we will use a multiple imputation method that incorporates predictive mean matching and flexible additive imputation models as implemented in the aregImpute function in the *Hmisc* R package. The impact of missing data on the validity of results will be examined with a pattern-mixture approach using the R package *SensMice*. This will be done for Aims 1 and 2. Additional secondary analyses will include: 1) multivariable modeling of participants who were excluded from the primary analysis due to the use of colchicine or steroids during the follow-up period (will examine clinical and biochemical endpoints); 2) multivariable modeling with adjustment for 2-HOBA levels for the clinical and biochemical endpoints; 3) multivariable modeling with adjustment for duration of smartwatch use.

Interim Analyses (Aim 1): An interim analysis will be performed by the study team and reviewed by the DSMB. When 50% of the target enrollment is reached testing for an association between 2-HOBA or placebo and significant adverse events (see Ethical Aspects of the Proposed Research for details), superiority and futility will be performed (see above: Sample Size and Power Aim 1). The interim analysis will include early stopping rules for superiority, futility, and harm.

- **Interim Analysis for Harm:** although none of our Phase I pre-clinical or clinical data have raised safety concerns, and no adverse events have been observed, we planned the assessment of safety which will be based mainly on the frequency of adverse events and on the number of laboratory values that fall outside of pre-determined ranges. Other safety data such as vital signs will be considered as appropriate. All safety data will be listed. Patients will be summarized by treatment and other covariates. All adverse events recorded during the study will be summarized. The incidence of treatment-emergent adverse events (new or worsening from baseline) will be summarized by body system, severity, type of adverse event, and relation to the investigational regimen. Severe adverse events and non-fatal serious adverse events are not expected.
- **Interim Analysis for Efficacy and Futility:** early stopping rules for efficacy and futility will be based on the primary endpoint in Aim 1, which is arrhythmia recurrence during the 28-day follow-up period. There will be no early stopping rules for the primary endpoints in Aim 2 (biochemical endpoint) or Aim 3 (pharmacogenomic analysis). Both of those aims will be considered exploratory.

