recurrence of AF. In the presence of 2-HOBA, IsoLG will preferentially bind to and therefore be inactivated by 2-HOBA thereby sparing injury to the atrial tissue caused by oxidative stress and its contribution to early recurrence of AF. Early recurrence of AF will be measured by ECGs that are recorded once per day by a smartwatch (Apple Watch, Apple Inc., Cupertino, CA) with additional ECGs recorded by the participant if they experience symptoms of AF, or if the smartwatch alerts the participant of a possible AF episode via its auto-detection AF monitoring algorithm. The Apple Watch's AF algorithm is based on sampling of heart rate and variability and will give an audible alarm if those parameters indicate a possible episode of AF. The smartwatch records a single-lead ECG if the participant touches the watch with their contralateral hand. The day and time of the episode is also stored by the smartwatch. At the end of the 28-day follow-up period, study personnel will review the stored ECGs. Blood will be drawn prior to ablation and on post-procedure Day 1 for measurement of IsoLG-adduct levels. DNA will be extracted to explore a pharmacogenomic interaction with haplotypes at the chromosome 4q25 AF risk locus, which: 1) is strongly associated with the development of AF and the early recurrence of AF after ablation²⁷; and 2) has been reported to be a regulator of an anti-oxidant gene program in response to cardiac injury.²⁸

The proposed double-blind, randomized, placebo-controlled trial of 2-HOBA in patients undergoing AF ablation is designed to address the following Specific Aims:

Specific Aim 1: To test the hypothesis that treatment with 2-HOBA reduces early recurrence of AF (clinical endpoint)

Specific Aim 2: To test the hypothesis that treatment with 2-HOBA reduces circulating levels of IsoLG-adducts (biochemical endpoint)

Specific Aim 3: To explore the idea that genetic variation at the 4q25 (*PITX2*) AF susceptibility locus modulates the clinical and biochemical response to 2-HOBA

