- A post ablation blood draw will be collected at the conclusion of the AF ablation prior to the central venous catheter removal. We will collect an additional 30 mL blood sample for research, with 10 mL of blood delivered to the Core Laboratory for Cardiovascular Translational and Clinical Research and 20 mL put in green top tubes and delivered to the research laboratory for culturing of monocytes and dendritic cells for measurement of isolevuglandin-adduct levels
- Following ablation, the patient will be extubated while in the operating room and returned to the EP holding room awake and alert.
- After removal of central venous catheters and when the patient is ready to begin eating and drinking, another dose of the study drug will be given.

Encounter 3: Post-ablation day #28

- The participant will be met in either the: 1) VHVI Arrhythmia Outpatient Clinic at the time of their 1-month Post-op Clinical Visit (Medical Center East or One Hundred Oaks locations), or 2) the VHVI Research Room.
- A 10 mL blood sample (divided between purple and blue top tubes) will be delivered to the Core Laboratory for Cardiovascular Clinical and Translational Research.
- The study personnel will record any ECGs recorded from the smartwatch from the day of the ablation until the end of the 28-day of follow-up period
- The study personnel will record remaining pills of either placebo or 2-HOBA at the conclusion of the study
- Participants will be allowed to keep the smartwatch
- Should the participant have required an iPhone as well as the smartwatch, the phone will be returned to the study personnel

Encounter 4: 6 and/or 12 month follow up visits

- Participants undergoing ablation are routinely seen at 6 and 12 months during follow up as part of clinical care
- During these visits, study team personnel may review medical records and meet with participants regarding clinical outcomes of their ablation procedure
- If 6 or 12 month follow up visits are not planned, study personnel may call patients during the 12 month time frame to see if any clinical events have occurred

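### The primary endpoint is any atrial arrhythmia recurrence within 28 days, but smartwatch ECGs are its only described source, so recurrences documented or cardioverted off the watch have no route into it

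*Combined protocol and SAP*

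**What the plan says.** The endpoint concept in Section 10.1 names no recording source: "early recurrence of AF, atrial tachycardia, or atrial flutter following AF ablation within 28 days follow-up".

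The measurement text names one source. Section 2.0 states: "Early recurrence of AF will be measured by ECGs that are recorded once per day by a smartwatch", with extra watch ECGs for symptoms or watch alerts. Section 10.1 (Measurement of Outcome) agrees: "For detection of the primary endpoint, participants will record a daily ECG each morning upon waking via the watch", again with watch ECGs on an alert or symptoms. It ends with the only rule for meeting the endpoint: "A continuous tracing of 30 seconds (the full duration of a Watch EKG tracing) will be considered as having met the primary endpoint".

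Collection follows the same line. At Encounter 3 (Day 28) in Section 6.0, the rhythm item is: "The study personnel will record any ECGs recorded from the smartwatch from the day of the ablation" to the end of follow-up. The other items are a blood sample, a pill count and arrangements for the devices. Review of medical records appears only at Encounter 4 (6 and/or 12 months), as an option: "study team personnel may review medical records and meet with participants regarding clinical outcomes of their ablation procedure".

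Cardioversion is foreseen, but only in the secondary AF-burden analyses of Section 10.1. The ordinal version is "ranked based on severity according to increasing AF burden and whether or not a cardioversion was performed".

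**The concern.** The concept is wider than the ascertainment. A participant who goes to an emergency department in AF, has it recorded on a 12-lead ECG and is cardioverted has had a recurrence in the sense of the primary hypothesis. If no 30-second watch tracing exists, nothing in the plan brings that event into the primary analysis. Yet the same cardioversion would affect the participant's rank in the ordinal secondary analysis.

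Two things are at stake. Treated recurrences are clinically important ones, and losing some of them lowers the event count in a trial with a stated power of only 81%. Also, with no written rule, someone must decide how to score such a participant after data exist.

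**Working it through.** **Tracing the event through the plan.** Take a participant with AF on a clinical ECG on Day 10 and no qualifying watch tracing.

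- Definition (10.1, first paragraph): the event fits the concept.
- Measurement (2.0; 10.1): only watch ECGs are named, so it is not captured.
- Collection (6.0, Encounter 3): no clinical ECG, telemetry or cardioversion is listed, so it is not collected for the endpoint.
- Analysis (10.1, Primary Analysis): all randomized participants enter with a yes/no outcome, and monitoring may be as low as 0 hours. Imputation is specified for covariates, not for this outcome.
- Secondary analysis (10.1): if cardioverted, the participant's ordinal rank reflects it.

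**The plan's own power.** Inputs from Section 10.1 (Sample size and power): n = 81 per arm, pc = 0.48, pt = 0.29, one-sided alpha 0.046 (z = 1.685). With p̄ = (pc + pt)/2:

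power = Φ{ [ (pc − pt) − z·√(2p̄(1 − p̄)/n) ] / √([pc(1 − pc) + pt(1 − pt)]/n) }

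Here p̄ = 0.385. The null standard error is √(2 × 0.385 × 0.615/81) = 0.0765 and the alternative standard error is √((0.2496 + 0.2059)/81) = 0.0750. So power = Φ[(0.19 − 1.685 × 0.0765)/0.0750] = Φ(0.816) = 79.3%. The unpooled variant gives 80.2%. The stated 81% is reproduced to within 2 points, so this point does not rest on an error in that figure.

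**Illustration of missed events.** Assumptions, none of them from the documents: 48% and 29% are rates from all sources, and the watch misses the same fraction m of recurrences in each arm. Both rates are then multiplied by (1 − m).

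| m | Placebo | 2-HOBA | Difference (points) | Power |
|---|---|---|---|---|
| 0 | 48.0% | 29.0% | 19.0 | 79.3% |
| 5% | 45.6% | 27.55% | 18.05 | 76.2% |
| 10% | 43.2% | 26.1% | 17.1 | 73.0% |
| 20% | 38.4% | 23.2% | 15.2 | 66.1% |

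The loss is 79.3 − 76.2 = 3.1 points at 5% and 79.3 − 73.0 = 6.3 points at 10%. The risk ratio does not move (0.29/0.48 = 0.604 in every row), because both rates shrink by the same factor. The odds ratio drifts from 0.442 to 0.464 at 10%.

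**Unequal misses.** Bias needs a difference between arms. If true recurrence were 48% in both arms and 10% of recurrences were missed in the 2-HOBA arm only (48.0% against 43.2%), the same formula gives Φ(−1.07), about 14% rejection instead of 4.6%. The reverse pattern gives about 1%. Nothing in the documents suggests such an imbalance, and treatment is double-blind.

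**The case against.** The strongest objection is that the plan never excludes these events. The 30-second sentence says what is sufficient and does not contain the word only. A reader might infer that a participant with off-watch AF is scored as having no recurrence. The documents do not say so: they are silent, and withdrawal by the PI (Section 9.0) or treatment as missing data is also conceivable. A reader might also infer that a cardioverted participant falls in the worst ordinal category. The plan gives no order of categories, so that is unsupported too. Both limits stand.

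The affected group is narrow. A participant using the watch would have to miss the morning ECGs, the AF and high-rate alerts and the symptom-prompted ECGs, yet have AF recorded or treated elsewhere. That leaves mainly people not wearing or not using the watch. This stands.

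The plan has partial safeguards. The primary model adjusts for hours of monitoring; there are a pattern-mixture analysis and an analysis adjusted for smartwatch use. Adverse event reporting (Section 8.0) covers worsening of the primary illness and hospitalization, and the ordinal analysis implies that cardioversions will be recorded somewhere. None of these counts the event as a primary recurrence.

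Finally, 48% can be read as the rate expected under the trial's own watch monitoring, since Section 10.1 extrapolates it from a 45% pilot rate obtained without continuous monitoring. On that reading, off-watch events already lie outside the 48%, and the power loss in the table is not a loss against the plan. This stands, and it is why the figures are illustrative only.

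Ascertainment by a single device on a uniform schedule is a defensible choice, but the plan does not say that it chose to leave clinically documented recurrences out.

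**Conclusion.** The concern holds as a gap between concept and ascertainment. The endpoint is any recurrence within 28 days, the only described source is the watch, and a recurrence documented or cardioverted elsewhere has no route in. That follows from the text and needs no assumption.

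The size is uncertain and probably small. The documents give no rate of off-watch recurrences. The loss of about 3 to 6 power points depends on an assumed 5% to 10% missed, equal misses in both arms, and reading 48% and 29% as all-source rates. There is no evidence of bias between arms. The case for change is that some recurrences left out would be clinically important, the scoring is open to judgement, and the remedy is cheap.

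**What to change.** Define the primary endpoint as AF, atrial flutter or atrial tachycardia occurring after the end of the ablation procedure and through Day 28, and shown by any of:

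- a 30-second watch tracing;
- a clinical 12-lead ECG;
- telemetry or another monitor, for at least 30 seconds;
- documentation as the indication for a cardioversion.

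The start time keeps rhythm and cardioversion during the procedure itself out of the endpoint. The duration rule keeps monitor evidence in line with the watch criterion.

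Add to Encounter 3 a medical-record check and a direct question to the participant about ECGs, monitoring and cardioversion since ablation. Have these events adjudicated blind to arm. Keep the watch-only definition as a prespecified sensitivity analysis.

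The cost is a few sentences of endpoint wording, a short record check at an encounter that already takes place, and blinded reading of a probably small number of tracings. The downside is that clinical ECGs are unscheduled, so ascertainment becomes less uniform between participants. Blinding makes a difference between arms unlikely, and the watch-only sensitivity analysis would show whether the choice matters.

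### The 81% power belongs to a one-sided 0.046 test; at the two-sided 0.041 level set for the final analysis, the same 162 patients give about 68%

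*Combined protocol and SAP*

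**What the plan says.** All the figures are in section 10.1 (Aim 1), in the paragraph on sample size and power.

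- Size and claim: "A total sample size of 162 with 81 in each arm will provide 81% power to detect a reduction".
- Assumed rates: "if the event rate is 29% in the treatment arm", against "a 48% rate of early recurrence in the placebo (control) group".
- Effect size: "This change corresponds to an odds ratio of 0.4 (treatment vs control").
- Test behind the power figure: "at the significance level of 0.046 using a 1-sided Farrington and Manning likelihood score test".
- Final analysis, once all patients "have completed their 28-day assessment of the primary point at two-sided significance level of 0.041".
- Interim look at 40 per group: the level is 0.006 in one sentence, and the efficacy boundary is p < 0.007 two sentences later. Neither is labelled one-sided or two-sided.
- Boundaries: the alpha- and beta-spending are said to follow O'Brien–Fleming.

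The primary-analysis paragraph names a chi-square comparison and a covariate-adjusted logistic model, and gives no level or sidedness for either. Sections 10.2 and 10.3 use a two-sided 5% level for Aims 2 and 3.

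**The concern.** A power statement is useful only if it refers to the test that decides the trial. Here the power was worked out for a test that spends 0.046 in the favourable tail, while the final analysis allows 0.0205 there. Nothing elsewhere in the document reconciles the two.

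The plan tells its readers, including the monitoring board, that the risk of missing the target effect is 19%. Under the stated final level it would be nearly one in three. There is also an interpretive risk. A one-sided p-value between 0.0205 and 0.046 fails the final-analysis sentence but would pass the test on which the trial was sized. That leaves room for argument after unblinding. An interim p-value between 0.006 and 0.007 is ambiguous in the same way, and that rule governs early stopping for efficacy.

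**Working it through.** **Inputs (section 10.1, sample size and power).** n = 81 per arm; placebo rate pC = 0.48; 2-HOBA rate pT = 0.29; interim at 40 per arm, so the information fraction is 80/162 = 0.494.

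**Formula.** With a null difference of zero, the Farrington–Manning score test is the pooled-variance test. Let d = pC − pT = 0.19 and p̄ = 0.385.

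- Null SE: s0 = √[2p̄(1 − p̄)/n] = √(2 × 0.385 × 0.615/81) = 0.0765
- Alternative SE: s1 = √{[pC(1 − pC) + pT(1 − pT)]/n} = √[(0.2496 + 0.2059)/81] = 0.0750
- Power = Φ[(d − z·s0)/s1] (pooled), or Φ(d/s1 − z) (unpooled)

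**Step 1: reproduce the plan's figure (one-sided 0.046, z = 1.685).** (0.19 − 0.1288)/0.0750 = 0.816, so power is 79.3%. The unpooled form gives 80.2% and exact binomial enumeration 79.2%. All are within two points of the stated 81%.

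**Step 2: the stated final level (two-sided 0.041, tail 0.0205, z = 2.0435).** (0.19 − 0.1563)/0.0750 = 0.450, so power is 67.4%. The unpooled form gives 68.8%, exact enumeration 68.5% and a Wald test on the log odds 66.3%. Adding an interim look at two-sided 0.006 gives 67.7% (pooled) or 69.2% (unpooled). Following the p > 0.4 futility rule takes the pooled value to 67.0%.

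**Step 3: what 81% would require at two-sided 0.041.** Keeping 29%: n = [2.0435 × √(2 × 0.385 × 0.615) + 0.878 × √(0.2496 + 0.2059)]²/0.19² = 110.7, so 111 per arm (222 in total). Keeping 81 per arm: a 2-HOBA rate of 26% (81.0% pooled), which is an odds ratio of (0.26/0.74)/(0.48/0.52) = 0.38.

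**Step 4: the odds ratio.** (0.29/0.71)/(0.48/0.52) = 0.4085/0.9231 = 0.44. An odds ratio of 0.4 means odds of 0.4 × 0.9231 = 0.369, which is a rate of 0.369/1.369 = 27.0%.

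| Test, 81 per arm | Power at 29% (pooled–unpooled) | Power at 27% (pooled–unpooled) |
|---|---|---|
| One-sided 0.046 | 79.3–80.2% | 86.5–87.3% |
| One-sided 0.05 | 80.4–81.3% | 87.3–88.2% |
| Two-sided 0.041 | 67.4–68.8% | 76.9–78.4% |
| Two-sided 0.05 | 70.4–71.7% | 79.4–80.7% |

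**Step 5: the boundaries.** These are nominal levels at information fraction 80/162, from the bivariate normal distribution with correlation √0.494.

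| Design | Interim | Final |
|---|---|---|
| Spending function of O'Brien–Fleming type (Lan–DeMets), one-sided 0.05 | 0.0053 | 0.0483 |
| Same, two-sided 0.05 | 0.0028 | 0.0491 |
| Classical O'Brien–Fleming, one-sided 0.05 | 0.0085 | 0.0468 |
| Same, two-sided 0.05 | 0.0049 | 0.0481 |
| Plan | 0.006 or 0.007 | 0.041 |

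No row has a final level near 0.041. Read as two-sided, 0.006 with 0.041 and 0.007 with 0.041 each spend about 0.044 in total. Read as one-sided, 0.006 with 0.046 spends 0.048.

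**The case against.** The strongest reply is that the 68% depends on a 29% treatment rate, while the plan also states an odds ratio of 0.4. If 27% was the real target, power at two-sided 0.041 is 77–78%, a shortfall of only three to four points. That range is correct and should be reported. It does not rescue the 81%, because at 27% the one-sided 0.046 test would have 86–87% power. The stated figure was evidently computed at 29%.

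Other replies stand in part:

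- The 0.046 is attached to the power calculation, and the only level stated for the final analysis is two-sided 0.041. Read strictly, there is one decision rule and a power claim that does not match it. Calling 0.046 a second final level stretches the text slightly.
- One-sided 0.05 also gives 80–81%. The gap comes from sidedness rather than from 0.046 in particular.
- The two-sided pair spends about 0.044, so following it would be conservative and would not inflate type I error.
- The primary analysis is an adjusted logistic model, whose power may differ. The documents give no covariate effects from which to calculate it, and the plan's own 81% also rests on an unadjusted test.
- O'Brien–Fleming need not mean the Lan–DeMets form. The plan does refer to spending functions, however, and 0.041 fits the classical boundaries no better.

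**Conclusion.** The concern holds. At the plan's own rates and sample size, power at the stated final level is 67–69%, some 12 to 14 points below the claimed 81%. The risk of missing the target effect is about 32% rather than 19%. No two-sided reading at 48% versus 29% reaches 81%; even two-sided 0.05 gives only 70–72%.

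This rests on an unadjusted two-proportion comparison, the stated 29% and 48%, and complete data on 81 per arm, since the sample-size text states no dropout allowance. If the effect is taken as an odds ratio of 0.4, the shortfall shrinks to three or four points but remains.

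The wrong odds ratio and the two interim values are smaller errors. They matter because they leave the intended design impossible to identify. This must be corrected before any analysis, because the sidedness of the primary test and the early-stopping threshold are both unsettled.

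**What to change.** Keep the two-sided test and the 162 patients, and make the paragraph agree with itself:

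- Replace 0.006, 0.007, 0.041 and 0.046 with one two-sided 0.05 pair of O'Brien–Fleming type, about 0.003 at 40 per arm and 0.049 at the end. Label both two-sided and name the spending function.
- Restate power for 29% versus 48% as about 70% (70.2% pooled, 71.5% unpooled with that pair).
- State that about 80% power corresponds to a 27% rate, odds ratio 0.4 (79.2–80.6%).
- Correct the odds ratio for 29% to 0.44.

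If the sponsor intended a one-sided 0.05 design, it should say so, delete the two-sided 0.041, and use about 0.005 and 0.048 throughout. Power at 29% is then 80–81%, and the present claim roughly stands. The odds ratio still needs correcting.

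Either route changes only protocol and SAP wording and needs no extra patients. The cost of the two-sided route is a less favourable power statement.
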